9.3.2. Allowed Medications

Use of the following medications is allowed during the study:

- oral diabetes medications if no changes in dose are made within 3 months before randomization (Visit T1/Day 1) or during the study;
- Intermediate-acting and long-acting insulin and insulin analogs when used for basal delivery of insulin including NPH, NovoLIN N, HumuLIN N, Glargine (Lantus), Determir (Levemir), NovoLIN 70/30, HumuLIN 70/30, NovoLog Mix 70/30 or HumuLOG Mix 70/30 if no changes in dose are made within 3 months prior to Visit T1;
- Rapid-acting and short-acting insulins only when used for basal infusion pump delivery (no bolus delivery allowed) including Lispro (HumaLog[®]), Aspart (Novolog[®]), Glulisine (Adipra[®]), Novolin R/Novolin Regular, Humulin R/Humulin Regular if no changes in dose are made within 3 months prior to Visit T1;
- obesity medications if no changes in dose have been made within 3 months before randomization (at Visit T1/Day 1) or during the study;
- hormone replacement therapy if no changes in dose are made within 5 weeks before randomization (at Visit T1/Day 1) or during the study;

- thyroid placement therapy if no changes in dose are made within 5 weeks before randomization (at Visit T1/Day 1) or during the study; and
- topical corticosteroids.

Short-term use of a medication for a self-limiting indication (eg, acetaminophen for a headache) may be authorized by the investigator. The maximum allowable dose of acetaminophen is 2 g/day. The investigator must make the decision to authorize use of such a medication only after consideration of the clinical situation, the potential for masking symptoms of a more significant underlying event, and whether use of the medication will compromise the outcome or validity of the study.

9.3.3. Contraception

Women of nonchildbearing potential are not required to use contraception. Women of nonchildbearing potential are defined as those who are naturally postmenopausal (defined as ≥ 1 year without menses and either a) ≥ 55 years old, or b) < 55 years with an FSH level ≥ 40.0 IU/L) and those who are surgically sterile by hysterectomy, bilateral oophorectomy, and/or tubal ligation.

Women of childbearing potential must use 1 acceptable method of birth control, minimally, from the time the ICF is signed through at least 30 days after the last dose of IMP. Acceptable methods of birth control include:

- a. placement of an IUD with or without hormones;
- b. established use of oral, implanted, topical, or injectable, or hormonal method of contraception associated with inhibition of ovulation;
- c. barrier methods, including condom or occlusive cap with spermicidal foam or spermicidal jelly;
- d. vasectomized male partner who is the sole partner for the subject; and
- e. true abstinence when this is in line with the preferred and usual lifestyle of the subject. Periodic abstinence (eg, calendar, ovulation, symptothermal, post-ovulation methods), declaration of abstinence for the duration of a trial, and withdrawal are not acceptable methods of contraception.

If a subject who is abstinent at the time the ICF is signed becomes sexually active, she must agree to use 1 acceptable method of contraception, as described above. There are no protocol-specific birth control requirements for men who have partners that can become pregnant. Contraceptive requirements do not apply to individuals who are exclusively in same-sex relationships.

9.4. Treatment Assignment, Randomization, and Blinding

During the Run-in Period, subjects will receive single-blind PBO beginning at Visit S2 and concluding with last dose on Day -1, the day prior to Visit T1. During the Treatment Period, subjects will receive double-blind IMP. On Day 1 (Visit T1), subjects will be randomized to receive either FDC or EZE or PBO, randomized 1:1:1. Randomized assigned blinded study drug will be dispensed to subjects according to the interactive web response system (IWRS). During

the Treatment Period, Sponsor, site personnel, contract research organization (CRO), and subject will all be unaware of subject's treatment assignment.

Blinding of treatment must be maintained for all subjects unless, in the opinion of the investigator, the safety of the subject may be at risk. Only under the rarest of circumstances should the investigator consider breaking the blind and only when medical/supportive care cannot be provided without determining if the subject is receiving active drug treatment. In the event that the blind needs to be broken prior to completion of the study, the investigator should contact the appropriate Medical Monitor by telephone. If the blind must be broken prior to consultation with the Medical Monitor, contact must be made within 24 hours of breaking the blind.

At the initiation of the study, the clinical site will be instructed on procedures for breaking the blind via the IWRS. In all cases of breaking the blind, the investigator must document in the subject's medical record the date, time, and reason for breaking the blind, and the names of personnel involved.

Post-randomization values for individual laboratory measures for LDL-C, hs-CRP, non-HDL-C, TC, TG, and HDL-C that may inadvertently suggest treatment assignment will not be available to personnel from the clinical site, the subject, the Sponsor, or the CRO. While knowledge of these values does not truly 'unblind,' the collection of these lab assessments by the investigator, all collaborating physicians, or the subjects locally (outside the study visits) is strongly discouraged. Investigators should not perform testing of these analytes at the local lab during the conduct of the study.

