11.4. Procedures and Schedule of Assessments

The study is comprised of two distinct periods: the Screening and Run-in Period and the Treatment Period. The schedule of study events is provided in [Appendix 1](#). However, a subject can be seen at any time for reasons of safety.

All relevant data will be captured on electronic case report forms (eCRFs) according to the eCRF completion guidelines.

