11.8. Subject Withdrawal Criteria

11.8.1. Early Withdrawal from Study

Subjects must remain in the study through Week 12 (Visit T3/Day 85 ± 3) to be considered as having completed the study. Subjects who prematurely withdraw from the study will be asked to continue to be followed for safety, as outlined in [Appendix 1](#).

Participation in the study is voluntary. Subjects may refuse or withdraw from participation in this study at any time and for any reason, specified or unspecified, and without penalty or loss of benefits to which the subject is otherwise entitled.

The investigator has the right and duty to interrupt the treatment of any subject whose health or well-being may be threatened by continued participation in this study. Such subjects should be withdrawn from the study and should not be continued under a modified regimen.

Subjects who are withdrawn from the study may not re-enter the study. The reasons for study withdrawal may include:

- Adverse event;
- Subject withdrawal of consent;
- Failure to comply with the protocol;
- Refusal to take IMP as indicated by the protocol;
- Illness, condition, or procedural complication that affects the subject's ability to participate in the study or that requires prohibited medication;
- Sponsor or investigator terminates the study;
- In the investigator's judgment, it is in the subject's best interest to discontinue participation in the study;
- Other (specify).

If a subject is lost to follow-up, study site personnel must make reasonable efforts to contact the subject to determine the reason for discontinuation/withdrawal. The measures that are taken to follow-up must be documented.

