13.6.3. General Monitoring and Management of Abnormal Clinical Laboratory Values

The investigator will review the results of all laboratory tests as they become available and will sign and date the report to document their review. The investigator will ascertain if any laboratory value is abnormal or represents a clinically significant change from baseline for the individual subject, with baseline defined as the last value or observation before the first dose of IMP. The investigator may repeat the laboratory test or request additional tests to verify the results of the original laboratory test.

If a laboratory value is determined to be an abnormal and clinically significant change from baseline for the subject, the investigator will determine if it qualifies as an AE (as described below), and if yes, an appropriate eCRF will be completed. All clinically significant laboratory abnormalities that occur during the study that were not present at baseline should be followed and evaluated with additional tests, if necessary, until diagnosis of the underlying cause or resolution. Specific monitoring and management guidelines for laboratories of special interest are outlined in the sections below.

An abnormal laboratory value that is not already associated with an AE is to be recorded as an AE only if any one of the following criteria is met:

- an action is taken with the imp because of the abnormality;
- intervention for management of the abnormality is required; or
- the abnormality be deemed clinically significant by the investigator.

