## 4.3 Randomization and Blinding

Subjects will receive single-blind PBO beginning at visit S2 and concluding with last dose on Day -1 (the day prior to Visit T1) during the Run-in period.

During the Treatment period, subjects will receive double-blind IMP. On Day 1 (Visit T1), subjects will be randomized to receive either FDC or EZE or PBO, randomized 1:1:1. Interactive web response system (IWRS) will be used to dispense randomized assigned blinded study drug to the subjects

Sponsor, site personnel, contract research organization (CRO), and subject will all be unaware of subject's treatment assignment during the Treatment period.

Blinding of treatment must be maintained for all subjects unless, in the opinion of the investigator, the safety of the subject may be at risk. Only under the rarest of circumstances should the investigator consider breaking the blind and only when medical/supportive care cannot be provided without determining if the subject is receiving active drug treatment. In the event that the blind needs to be broken prior to completion of the study, the investigator should contact the appropriate Medical Monitor by telephone. If the blind must be broken prior to consultation with the Medical Monitor, contact must be made within 24 hours of breaking the blind.

Confidential

Page 13 of 38

Version 1.3, July 23, 2019 Statistical Analysis Plan

At the initiation of the study, the clinical site will be instructed on procedures for breaking the blind via the IWRS. In all cases of breaking the blind, the investigator must document in the subject's medical record the date, time, and reason for breaking the blind, and the names of personnel involved.

Post-randomization values for individual laboratory measures for LDL-C, hs-CRP, non-HDL-C, TC, TG, and HDL-C that may inadvertently suggest treatment assignment will not be available to personnel from the clinical site, the subject, the Sponsor, or the CRO.

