#### 5.5.3 Laboratory Evaluations

Continuous laboratory parameters (serum chemistry, hematology, coagulation, urinalysis, urinalysis [microscopic]) listed in Table 2; fasting serum glucose, and HbA1c will be summarized using descriptive statistics for the observed value and the change, percent change from baseline. Missing values for any of the safety laboratory evaluations will not be imputed; that is, only observed case data will be used. Baseline is defined as the last value prior to the first dose of study medication. Categorical urinalysis data will be listed, but will not be summarized.

As part of the AESI evaluation, below safety lab abnormality will be summarized by treatment group. All post-baseline lab values are being considered. Further details are provided in Section 5.5.3.1 through 5.5.3.4.

- ALT or AST (> 3x ULN and >5xULN)
- TB (> 2x ULN)
- Potential Hy's Law case: (ALT and/or AST > 3xULN with concurrent TB > 2xULN)
- CK (> 5x ULN) and (>10x ULN)
- Fasting Serum Glucose (mg/dL) ( $\leq$ 50, and  $\geq$ 126)
- HbA1C ( $\geq x\%$ ) (the median of HbA1C at baseline)
- Creatinine (change from baseline for >1 mg/dL)
- eGFR (< 15 mL/min/1.73m^2, 15 -< 30 mL/min/1.73m^2)
- Hgb (g/dL) (decrease from baseline for  $\geq 2$  g/dL)
- Hgb (<8 g/dL)

Confidential

Page 24 of 38

Version 1.3, July 23, 2019 Statistical Analysis Plan

• Table 2: Clinical Laboratory Parameters (Safety)

The number and percentage of patients with laboratory abnormalities (i.e., laboratory values outside the stated laboratory normal range) will be summarized at each time point (i.e., including baseline and post-baseline time points) for each laboratory parameter. The determination of laboratory abnormalities will take into account any unscheduled

Confidential

Page 25 of 38

Esperion Therapeutics, Inc.Version 1.3, July 23, 2019Protocol: 1002FDC-058Statistical Analysis Plan

laboratory assessments. Additional lab-related summaries will be provided as follows for hepatic safety, musculoskeletal safety, diabetes and glycemia, and renal safety.

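### Protocol 9.4 masks post-randomisation triglycerides with no visible exception for a severe value, so a silent severe rise at T2 need not reach a physician before T3; the effect is small and the repair is one sentence

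*Protocol*

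**What the plan says.** Protocol 9.4 covers LDL-C, hs-CRP, non-HDL-C, TC, TG and HDL-C. It describes their post-randomisation values as ones "that may inadvertently suggest treatment assignment" and states that they "will not be available to personnel from the clinical site, the subject, the Sponsor, or the CRO". On local testing it says: "Investigators should not perform testing of these analytes at the local lab during the conduct of the study". For collaborating physicians and subjects, local collection is strongly discouraged rather than barred. SAP 4.3 repeats the masking for "Post-randomization values for individual laboratory measures for LDL-C, hs-CRP, non-HDL-C, TC, TG, and HDL-C", also without an exception.

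Other text bears on whether a severe TG value could still surface:

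- **Blind-break rule (Protocol 9.4).** It releases the treatment assignment when safety requires it.
- **Laboratory review (Protocol 13.6.3).** "The investigator will review the results of all laboratory tests as they become available". The investigator may also repeat a test or ask for others.
- **Unscheduled contact (Protocol 11.4).** "a subject can be seen at any time for reasons of safety".
- **Withdrawal (Protocol 11.8.1).** The listed reasons include a condition that affects the subject's "ability to participate in the study or that requires prohibited medication".
- **TG limits.** TG above 400 mg/dL at S3 excludes the subject (Protocol 8.2). In the Synopsis, TG above 400 mg/dL triggers a direct LDL-C assay for the analyses.
- **Lipid therapy.** It stops at S2 (Protocol 11.6.2) and may restart at the end of T3 (Protocol 11.7.3).

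**The concern.** The subjects have type 2 diabetes with HbA1c of 7% to 10% at screening. The protocol takes them off fibrates, niacin and omega-3 products along with all other lipid therapy. Before randomisation, TG above 400 mg/dL is a reason not to enrol. After randomisation, the same or a higher value has one stated consequence, which is a different LDL-C assay. If the masking is applied as written, the laboratory can hold a severe T2 result that nobody responsible for the subject has seen. Withdrawal for rescue treatment is available, but someone must first know that rescue is needed.

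What is at stake is the safety of a very small number of subjects. The primary LDL-C comparison is not affected.

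**Working it through.** **1. Is there a visible release route?**

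- The blind-break rule releases the treatment code, not a lipid value, and presupposes that the investigator already suspects a problem.
- The general review duty in Protocol 13.6.3 attaches to results that become available. Masked TG does not.
- Protocol 13.6.3.1 to 13.6.3.5 give management rules for liver tests, creatinine and eGFR, haemoglobin, CK, and hypoglycaemia with acidosis. None covers TG.
- TG is in Protocol Table 2 (lipids), not Table 3 (safety laboratories).
- SAP 5.5.3 introduces its threshold list with "As part of the AESI evaluation, below safety lab abnormality will be summarized by treatment group". The list has no TG level, and SAP Appendix 2 has no TG term.

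No release route is visible.

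**2. How long is the interval?**

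T2 is Day 28 ± 3 and T3 is Day 85 ± 3.

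- Target days: 85 − 28 = 57 days.
- Shortest: 82 − 31 = 51 days.
- Longest: 88 − 25 = 63 days.

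This is the time to the next scheduled lipid draw. It is not a time to disclosure, because T3 TG is also post-randomisation and masked.

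**3. What can the site already see?**

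The masking covers post-randomisation values only. S3 is about 4 weeks and T1 about 5 weeks after lipid therapy stops. In Protocol 11.7.1 the T1 lipid sample comes before randomisation and the first dose. On a plain reading, then, the site has two off-therapy TG values.

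**4. How many subjects?**

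The documents give no TG distribution and no TG harm level, so every input here is an assumption:

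- median TG 150 or 180 mg/dL;
- between-subject SD of log TG 0.40 or 0.50;
- within-subject SD of log TG 0.20 or 0.30;
- no drug effect on TG;
- 500 mg/dL as an example of a severe value, and 300 mg/dL as an example of a value that would catch a physician's eye.

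Model: log TG at a visit = subject mean + independent visit noise, keeping only subjects with S3 TG ≤ 400 mg/dL. The eight combinations were simulated with millions of subjects each. Expected count = N × p, and the chance of at least one = 1 − (1 − p)^N. N is 168 in the protocol and 234 in the SAP.

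| Quantity | Range over scenarios | N = 168 | N = 234 |
|---|---|---|---|
| p(T2 > 500) | 0.0014 to 0.0169 | 0.2 to 2.8 subjects | 0.3 to 4.0 subjects |
| p(repeat > 500, given T2 > 500) | 12% to 21% | | |
| p(both > 500) | 0.00019 to 0.0036 | 0.03 to 0.60 subjects | 0.04 to 0.84 subjects |
| Chance of at least one with both > 500 | | 3% to 45% | 4% to 57% |
| p(T2 > 1000) | at most about 0.00016 | at most 0.03 subjects | at most 0.04 subjects |

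Of the subjects above 500 mg/dL on both draws, 90% to 99% already had TG above 300 mg/dL at S3 or T1. At the upper end, 0.84 × 10% = 0.08, so the expected number of persistent cases with no warning at either visit is below one tenth of a subject.

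**The case against.** The strongest reply has four parts.

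**The site is not blind to TG.** It sees S3 and T1 values taken off therapy, and S3 is capped at 400 mg/dL. This stands, and it is the main reason the point is small. It does not close the gap: a warning value before randomisation does not tell anyone that T2 was severe.

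**An alert may already exist.** Samples are handled under a central-laboratory manual, which is a natural home for alert rules. The manual and Administrative Change Letter #1 were not supplied, and Protocol 13.7.3 is partly redacted. The central laboratory is not among the parties masked in 9.4. This also stands. A reader might infer that the trial has no TG safeguard at all, but the documents support only that none is visible and that 9.4 points to none.

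**Other routes remain.** Unscheduled visits (11.4), additional tests (13.6.3) and a departure agreed with the medical monitor (19.3) are all open, and outside testing by other physicians is only discouraged. A reader might infer that investigators are powerless. They are not, once a problem is suspected. What is left is a rise without symptoms. Adverse-event review and the unmasked T2 results, such as glucose, HbA1c and apoB, do not report TG.

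**The rates are assumed, and most alerts would not repeat.** Correct on both counts. With 12% to 21% of single values above 500 mg/dL repeating, 79% to 88% would not. That argues for choosing the threshold with care and leaving the repeat to the investigator.

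**Conclusion.** The point holds as a low-priority safety improvement. The masking rule in Protocol 9.4 and SAP 4.3 has no visible exception, so a silent severe TG value at T2 can go unseen for 57 days (51 to 63), and no visible text releases the T3 value.

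The size is small. Under the assumed distributions, 0.1% to 1.7% of subjects have a single T2 value above 500 mg/dL, and fewer than one subject in the trial is expected to exceed it twice. Most of those would already have looked high before randomisation. These figures depend on the assumed median, spread and thresholds, and on no arm raising TG; nothing visible in the documents suggests that one does.

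Two stronger readings should be resisted. The masking is not itself a fault, because TG is a secondary endpoint and 9.4 gives a fair reason for withholding it. Nor does the gap threaten the primary result.

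**What to change.** Keep the masking and add one sentence to Protocol 9.4, mirrored in SAP 4.3. It should say that when a post-randomisation fasting TG exceeds a severe threshold fixed in advance, the central laboratory sends the investigator a TG-only alert and releases no other lipid value. The threshold might be 500 mg/dL, or higher to limit false alerts. The investigator may then repeat the test under 13.6.3 and use the existing options: closer follow-up under 11.4, or withdrawal under 11.8.1 if prohibited medication is needed. If the laboratory manual already contains such an alert, a cross-reference in 9.4 is enough.

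The cost is one sentence and one alert setting at a laboratory that already has to act on TG above 400 mg/dL for the direct LDL-C assay. There is no new role and no new scheduled visit. The downside is that the TG status of roughly 0 to 4 subjects becomes known to the site, mostly for single values that would not repeat. The blinding risk is small: 9.4 says these values may hint at assignment, but also that knowing them is not true unblinding.

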9.5. Investigational Medicinal Product Adherence

Subjects will be instructed to bring their IMP to each study visit beginning at Visit S3 and completing at Visit T3/EOS. Compliance with dosing instructions will be assessed by counting the number of tablets and capsules remaining at each study visit. If the subject has not taken multiple doses as instructed, the subject will be queried for a reason, findings will be documented, and the subject will be counseled on the importance of carefully following all dosing instructions. Factors contributing to poor adherence will be determined and, if possible, remedied. Subjects demonstrating poor adherence during the Treatment Period will continue to be counseled on the importance of carefully following all dosing instructions, but will not be removed from the study.

9.6. Overdose

There is no specific antidote for an overdose of BA. Management of an overdose should be focused on the treatment of symptoms. These symptoms should be managed according to current standards of care with appropriate supportive measures. Discontinuation of study drug should also be considered, as per medical judgement.

Ezetimibe has been generally well tolerated in clinical trials in which healthy subjects (N = 15) received 50 mg/day of EZE for 14 days, subjects with primary hyperlipidemia (N = 18) received 40 mg/day of EZE for up to 56 days, and subjects with homozygous sitosterolemia (N = 27) received 40 mg/day of EZE for up to 26 weeks.¹⁴ One female subject with homozygous

sitosterolemia took an accidental overdose of EZE 120 mg/day for 28 days with no reported clinical or laboratory AEs. Symptomatic and supportive measures should be employed in the event of overdose.

